7.1.5 Study Treatment

Abemaciclib will be given as a single oral agent. The starting dose will be 200 mg twice daily. One cycle = 28 days. There will be no protocol scheduled hiatus and daily dosing will be continuous unless there is unacceptable toxicity, disease progression, or death.

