7.1.6 Dosing Adjustments, Delays and Discontinuation

Abemaciclib Dose Modification for Grade 3 or 4 AEs

| Dose Level | Abemaciclib Dose |
|---------------------------|--------------------|
| Recommended starting dose | 200 mg twice daily |
| First dose reduction | 150 mg twice daily |
| Second dose reduction | 100 mg twice daily |
| Third dose reduction | 50 mg twice daily |

Complete blood counts with differentials and complete metabolic panel will be monitored every 2 weeks for the first 2 months, then monthly for the next 2 months, at the beginning of every cycle.

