7.3.8 Dose Delays/Modifications

Dose Modifications for Adverse Reactions

The recommended abemaciclib dose modifications for adverse events are provided in table below. Discontinue abemaciclib for participants unable to tolerate 50 mg twice daily. Once the drug is reduced, there is no dose re-escalation.

Abemaciclib Dose Modification for Adverse Reactions

| Dose Level | Abemaciclib Dose |
|---------------------------|--------------------|
| Recommended starting dose | 200 mg twice daily |
| First dose reduction | 150 mg twice daily |
| Second dose reduction | 100 mg twice daily |
| Third dose reduction | 50 mg twice daily |

Guidelines for Dose Adjustments and Delays of Abemaciclib

| Toxicity Type | Toxicity Profile and Severity | Dose Modification | Dose Reduction |
|--------------------------------------------------|----------------------------------|---------------------------------------------------------|------------------------------------------------------------------------------------------------------------------------------------------|
| Hematologic Toxicity | Grade 3 | Dose MUST be held until toxicity resolves to ≤ Grade 2. | Dose MAY be reduced by 1 dose level at investigator's discretion. |
| Hematologic Toxicity (second or more recurrence) | Grade 3 | Dose MUST be held until toxicity resolves to ≤ Grade 2. | Dose MUST be reduced by 1 dose level with each occurrence. Discontinue abemaciclib for participants unable to tolerate 50 mg twice daily |
| Hematologic Toxicity | Grade 4 | Dose MUST be held until toxicity resolves to ≤ Grade 2. | Dose MUST be reduced by 1 dose level. Discontinue abemaciclib for participants unable to tolerate 50 mg twice daily |

| Nonhematologic Toxicity (except diarrhea and ALT increased) | Persistent or recurrent Grade 2 that does not resolve with maximal supportive measures within 7 days to baseline or Grade 1 | Dose MUST be held until toxicity resolves to either baseline or ≤ Grade 1. | Dose MUST be reduced by 1 dose level. Discontinue abemaciclib for participants unable to tolerate 50 mg twice daily |
|----------------------------------------------------------------------|-----------------------------------------------------------------------------------------------------------------------------|----------------------------------------------------------------------------|-----------------------------------------------------------------------------------------------------------------------------|

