| Nonhematologic Toxicity (except diarrhea and ALT increased) | Grade 3 or 4 that does not resolve with maximal supportive measures within 7 days to baseline or Grade 1 | Dose MUST be held until toxicity resolves to either baseline or ≤ Grade 1. | Dose MUST be reduced by 1 dose level. Discontinue abemaciclib for participants unable to tolerate 50 mg twice daily |
| Diarrhea | Grade 2 that does not resolve within 24 hrs to at least Grade 1 | Dose MUST be held until toxicity resolves to \(\leq \text{Grade} \) 1. | Dose MAY be reduced by 1 dose level. |
| Diarrhea | Grade 3 or 4 that does not resolve with maximal supportive measures within 7 days or requires hospitalization. | Dose MUST be held until toxicity resolves to ≤ Grade 1. | Dose must be reduced by 1 dose level - Discontinue abemaciclib for participants unable to tolerate 50 mg twice daily |

| ALT/AST increased | Grade 2 (>3.0-5.0xULN) that does not resolve within 7 days to baseline or < Grade 1 | Dose MUST be held until toxicity resolves to baseline or Grade 1 | Dose MUST be reduced by 1 dose level |
|-------------------|-------------------------------------------------------------------------------------|------------------------------------------------------------------|------------------------------------------|
| | Grade 3 (>5.0-20.0xULN) with total bilirubin >2xULN, in the absence of cholestasis | Abemaciclib therapy MUST be discontinued | Abemaciclib therapy MUST be discontinued |
| | Grade 4 (>20.0xULN) | Abemaciclib therapy MUST be discontinued | Abemaciclib therapy MUST be discontinued |

Abbreviations: ALT = alanine aminotransferase, AST=aspartate aminotransferase, ULN = upper limit of normal.

Monitor ALT, AST, and serum bilirubin prior to the start of abemaciclib therapy, every 2 weeks for the first 2 months, monthly following cycle 2, and as clinically indicated.

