7.4.5 General Guidance for Interstitial lung disease (ILD)/Pneumonitis events

Interstitial lung disease (ILD) / pneumonitis has been identified as an adverse drug reaction for abemaciclib. Adverse events reported included events such as interstitial lung disease, pneumonitis, obliterative bronchiolitis, organizing pneumonia, pulmonary fibrosis. The majority of events were Grade 1 or Grade 2 with serious cases and fatal events reported.

Monitor for clinical symptoms or radiological changes indicative of ILD/pneumonitis and please ask patients to report any new or worsening pulmonary symptoms. Symptoms may include hypoxia, cough, dyspnea, or interstitial infiltrates on radiologic exams.; these symptoms should be investigated and treated as per local clinical practice and/or guidelines (including corticosteroids as appropriate). Infectious, neoplastic, and other causes for such symptoms should be excluded by means of appropriate investigations. Investigations may include imaging such as high resolution computer tomography (HRCT), bronchoalveolar lavage (BAL), and biopsy as clinically indicated (see also Table 7: refer to dose adjustment table for interstitial lung disease/pneumonitis).

Dose Modification and Management — Interstitial Lung Disease/Pneumonitis

| ose mounication and managem | ent interstitut Eung Disease/I neumonitis |
|--------------------------------------------------------------------------------------------------------------------------------------|--------------------------------------------------------------------------------------|
| CTCAE Grade | Abemaciclib Dose Modifications |
| Grade 1 or 2 | No dose modification is required. |
| Persistent or recurrent Grade 2 toxicity that does not resolve with maximal supportive measures within 7 days to baseline or Grade 1 | Hold dose until toxicity resolves to baseline or Grade 1. Resume at next lower dose. |
| Grade 3 or 4 | Discontinue abemaciclib. |

Dose Modification and Management — Nonhematologic Toxicities Excluding Diarrhea, ALT Increased, and ILD/Pneumonitis

| CTCAE Grade | Abemaciclib Dose Modifications |
|---------------------------------------------------------------------------------------------------------------------------------------------------|---------------------------------------------------------------------------------------|
| Grade 1 or 2 | No dose modification is required. |

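### The dose-modification table in 7.3.8 has no row for isolated Grade 3 ALT, so unresolved Grade 2 ALT carries a mandatory hold and permanent reduction while ALT first found at Grade 3 carries neither

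*Combined protocol and SAP*

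**What the plan says.** Section 7.3.8 sets mandatory dosing actions by toxicity. Its ALT/AST block has three triggers:

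- "Grade 2 (>3.0-5.0xULN) that does not resolve within 7 days to baseline or < Grade 1": the dose must be held until baseline or Grade 1 and then reduced by one level.
- "Grade 3 (>5.0-20.0xULN) with total bilirubin >2xULN, in the absence of cholestasis": abemaciclib must be discontinued.
- Grade 4 (above 20xULN): abemaciclib must be discontinued.

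Reductions are permanent: "Once the drug is reduced, there is no dose re-escalation".

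The general rows of the same table are labelled "Nonhematologic Toxicity (except diarrhea and ALT increased", and the second general table, in 7.4.5, is headed "Nonhematologic Toxicities Excluding Diarrhea, ALT Increased, and ILD/Pneumonitis". Neither applies to ALT.

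Other sections also bear on a raised ALT:

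- **3.4** withdraws a participant for toxicity that the investigator finds unacceptable, or for possibly related toxicity unresolved in 14 days.
- **7.1.5** says that "daily dosing will be continuous unless there is unacceptable toxicity, disease progression, or death".
- **7.1.6** is headed "Abemaciclib Dose Modification for Grade 3 or 4 AEs" but lists dose levels only.
- **7.4.3** asks for repeat liver tests in 3 to 5 days at ALT 8xULN, or at ALT 5xULN with bilirubin 2xULN.
- **10.1.1** requires immediate cessation when AST or ALT is at least 3xULN with bilirubin at least 2xULN or INR above 1.5, for liver injury that may be drug-induced.

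Under 7.3.8, ALT, AST and bilirubin are checked "every 2 weeks for the first 2 months, monthly following cycle 2, and as clinically indicated".

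**The concern.** A dose-modification table should not become weaker as the event becomes more severe. Here a participant with ALT at 4xULN that has not settled in a week must stop and restart one level lower for good. A participant whose ALT is first found at 6xULN, with normal bilirubin and INR, can stay on 200 mg twice daily without any departure from the table. No rationale for this ordering is given.

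The stake is participant safety and consistent dosing, not the response-rate analysis. Section 2.4.2 reports Grade 3 ALT increases with abemaciclib and attributes two deaths in the fulvestrant combination study to hepatotoxicity. Section 3.1 admits participants with liver metastasis at AST/ALT up to 5xULN, the lower edge of the uncovered band. Section 7.1.3 allows sites to be added, so a rule left to individual judgement could be applied differently across sites.

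**Working it through.** **Inputs.** Grade bands, triggers and actions come from 7.3.8; the exclusions from 7.3.8 and 7.4.5; the cessation rule from 10.1.1; repeat testing from 7.4.3; withdrawal from 3.4; entry limits from 3.1. The plan states no figure to reproduce, so the check is one of rule coverage.

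**Step 1: apply every numerical ALT rule to example cases.** Bilirubin is 1xULN and INR is 1 unless stated.

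| ALT (xULN) | Other values | Days unresolved | What the protocol requires |
|---|---|---|---|
| 4 | | 8 | Hold and reduce one level (7.3.8) |
| 6 | | 0 or 8 | No rule applies |
| 10 | | 8 | Repeat tests only (7.4.3) |
| 19 | bilirubin 1.9xULN, INR 1.5 | 14 | Repeat tests only (7.4.3) |
| 10 | | 15 | Repeat tests (7.4.3); withdrawal if possibly related (3.4) |
| 10 | bilirubin 2xULN | 0 | Cessation (10.1.1), repeat tests (7.4.3) |
| 10 | INR 1.6 | 0 | Cessation (10.1.1), repeat tests (7.4.3) |
| 21 | | 0 | Discontinue (7.3.8), repeat tests (7.4.3) |

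The uncovered region is ALT above 5 and up to 20xULN with bilirubin below 2xULN and INR at most 1.5.

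**Step 2: how long the gap lasts.** The Grade 2 row acts after 7 days, and the fixed limit in 3.4 acts at 14 days. For a possibly related event the difference in mandate therefore covers about days 8 to 14, after which 3.4 is the stricter rule. For an event judged unrelated, 3.4 sets no time limit, whereas the Grade 2 row states no attribution condition. If ALT falls back to Grade 2 and stays there, the Grade 2 row applies from then.

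**Step 3: the AST case.** The general Grade 3 or 4 row in 7.3.8 excludes ALT but does not name AST. Read literally, Grade 3 AST unresolved in 7 days must be held and reduced. The clearest gap is Grade 3 ALT without Grade 3 AST.

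**Step 4: distance from the entry limit.** The rise needed to reach 5xULN from a starting value b is 5/b - 1. From 3xULN it is 5/3 - 1 = 67%; from 4xULN, 5/4 - 1 = 25%; from 5xULN, 5/5 - 1 = 0, so any rise enters the band. The documents do not say how many participants will start near the limit.

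**Step 5: frequency, for context only.** The chance of at least one case among n participants is 1 - (1 - p)^n. Table 4 (monotherapy, breast cancer) gives Grade 3 ALT in 3%, and Table 2 (with fulvestrant) in 4%. The 1% is an assumption, to allow for the uncovered case being only part of all Grade 3 ALT.

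| p | n = 10 | n = 20 |
|---|---|---|
| 1% (assumed) | 1 - 0.99^10 = 10% | 1 - 0.99^20 = 18% |
| 3% (Table 4) | 1 - 0.97^10 = 26% | 1 - 0.97^20 = 46% |
| 4% (Table 2) | 1 - 0.96^10 = 34% | 1 - 0.96^20 = 56% |

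The tabulated rates cover Grade 3 ALT at any bilirubin and come from another disease. They neither bound nor estimate the rate of the uncovered case in biliary cancer.

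**The case against.** The strongest reply is that safety does not rest on this table alone. The investigator can stop treatment at any time for unacceptable toxicity (3.4, 7.1.5), the dose ladder in 7.1.6 makes reduction available, repeat tests apply from ALT 8xULN, and the data safety monitoring committee reviews all safety data after five participants. For possibly related events the 14-day rule limits the gap and is then stricter than a hold. All of this stands and keeps the point modest. None of it requires a hold or reduction for isolated ALT while it remains at Grade 3 within those 14 days.

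The test schedule is not an argument for the gap either. Scheduled tests are 14 days apart in cycles 1 and 2 and 28 days apart later, so the Grade 2 row's 7-day check also depends on an unscheduled test.

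A reader might infer three stronger claims that the documents do not support:

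- **That no Grade 3 transaminase rise has a dosing rule.** Grade 3 AST can be read into the general row, and Table 4 shows Grade 3 AST (4%) to be no rarer than Grade 3 ALT (3%).
- **That staff will probably need the missing row.** No rate is given for the uncovered case, and closeness to the entry limit says nothing about how many participants start there.
- **That 7.3.8 and 10.1.1 conflict over cholestasis.** Section 10.1.1 concerns liver injury that may be drug-induced, so a rise explained by obstruction can naturally fall outside it. That is consistent with the exception in 7.3.8.

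**Conclusion.** The concern holds for isolated Grade 3 ALT: above 5 and up to 20xULN, bilirubin below 2xULN, INR at most 1.5. Followed as written, the table mandates a hold and permanent reduction for the milder unresolved event and neither for the more severe one. The inversion ends when the investigator judges the toxicity unacceptable, when ALT falls to a persistent Grade 2, or at 14 days if the event is possibly related. It is narrower when AST is also Grade 3.

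Confidence is high that the row is missing, since the Grade 2, 3 and 4 entries read as complete with no sign of a lost row. How often it will matter is unknown. The conclusion rests on the text of the rules and not on any assumed rate. The sponsor should correct this because it concerns participant safety and costs little. It does not affect the sample size, endpoints or analysis.

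**What to change.** Add an ALT/AST row to 7.3.8 for Grade 3 that does not meet the discontinuation criteria, at least as strict as the Grade 2 row: hold until baseline or Grade 1, then reduce by one dose level. State whether the hold starts at once or after at most 7 days. Require a repeat liver test within 3 to 5 days, extending down to 5xULN what 7.4.3 already asks from 8xULN.

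Together with that row, change the exclusions in the general rows of 7.3.8 and in the 7.4.5 table to *ALT/AST increased*, so that both enzymes follow one block. The label should not be changed without the row, because that would remove the cover that Grade 3 AST can now be read to have.

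The cost is amendment wording, an occasional extra liver test for participants who reach Grade 3, and some additional holds or reductions, which are permanent under the existing rule. Scheduled visits are unchanged.

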7.4 Supportive Care Guidelines

7.4.1 Guidelines for Diarrhea Management

Clinical trial data indicates the majority of patients who receive abemaciclib will develop diarrhea. Early identification and intervention for the management of diarrhea has been helpful to patients

At enrollment, participants should receive instructions on the prompt management of diarrhea. In the event of diarrhea, supportive care measures should be initiated as early as possible. These include the following:

- At the first sign of loose stools, the participant should initiate antidiarrheal therapy (e.g. loperamide) and notify the investigator for further instructions and appropriate follow-up.
- Participants should also be encouraged to drink fluids (e.g., 8 to 10 glasses of clear liquids per day).
- Site personnel should assess response within 24 hours.
- (Refer to Dose Modification Table above for more information on dose modification).

7.4.2 Guidance for Increases in Serum Creatinine and Assessment of Renal Insufficiency

Abemaciclib has been shown to increase serum creatinine due to inhibition of renal tubular secretion of creatinine without affecting glomerular function. In vitro studies have indicated that abemaciclib and its major metabolites LSN2839567 and LSN3106726 inhibit the renal transporters OCT2, MATE1, and MATE2-K at clinically relevant concentrations. Thus, increases in serum creatinine observed following dosing with abemaciclib, in the absence of simultaneous increases in BUN or

development of an abnormal urinalysis, are most likely due to inhibition of its tubular secretion via OCT2, MATE1, and MATE2-K and may not reflect a decline in renal function, making serum creatinine level an unreliable measurement for renal function.

Increases in serum creatinine occurred within the first 28-day cycle of dosing remained stable through the treatment period and were reversible upon treatment discontinuation.

If deterioration of renal function is suspected, measures other than those relying on assessment of serum creatinine should be used to determine renal function. No dosage adjustment is required for patients with mild or moderate renal impairment (CLcr \geq 30-89 mL/min, estimated by Cockcroft-Gault [C-G]). The pharmacokinetics of abemaciclib in patients with severe renal impairment (CLcr \leq 30 mL/min, C-G), end stage renal disease, or in patients on dialysis is unknown; hold abemaciclib unless Clcr improves to \geq 30 mL/min.

7.4.3 General Guidance for Hepatic Monitoring

To ensure patient safety the investigator should collect specific recommended clinical information and follow-up laboratory tests as shown below in Table 5.

Details for hepatic monitoring depend upon the severity and persistence of observed laboratory test abnormalities. If a study patient experiences elevated ALT 5×ULN and elevated total bilirubin (TB) 2×ULN, or ALT 8×ULN, liver tests, including ALT, AST, direct bilirubin, gamma-glutamyl transferase (GGT), and creatine phosphokinase (CPK), should be repeated within 3 to 5 days to confirm the abnormality and to determine if it is increasing or decreasing. If the abnormality persists or worsens, clinical and laboratory monitoring should be initiated by the investigator, based on the hepatic monitoring tests below.

Table 5 Hepatic Monitoring Tests for a Hepatic Treatment Emergent Abnormality.

| Hepatic Hematology | Haptoglobin |
|----------------------------------|---------------------------------|
| Hemoglobin | • |
| Hematocrit | Hepatic Coagulation |
| RBC | Prothrombin Time |
| WBC | Prothrombin Time, INR |
| Neutrophils, segmented and bands | |
| Lymphocytes | Hepatic Serologies ^a |
| Monocytes | Hepatitis A antibody, total |
| Eosinophils | Hepatitis A antibody, IgM |
| Basophils | Hepatitis B surface antigen |
| Platelets | Hepatitis B surface antibody |
| | Hepatitis B Core antibody |
| Hepatic Chemistry | Hepatitis C antibody |
| Total bilirubin | Hepatitis E antibody, IgG |
| Direct bilirubin | Hepatitis E antibody, IgM |
| Alkaline phosphatase | |
| ALT | Anti-nuclear antibody |
| AST | Anti-actin antibody |
| GGT | Anti-smooth muscle antibody |
| CPK | · |

Abbreviations: ALT = alanine aminotransferase; AST = aspartate aminotransferase; CPK = creatine phosphokinase; GGT = gamma-glutamyl transferase; Ig = immunoglobulin; INR = international normalized ratio; RBC = red blood cells; WBC = white blood cells.

a Reflex/confirmation dependent on regulatory requirements and/or testing availability.

7.4.4 General Guidance for Hematology Toxicity

7.4.4.1 Neutropenia

Severe (Grade 3 and 4) neutropenia was observed in participants receiving abemaciclib-see Tables 1-4. If a participant requires blood cell growth factors, these should be administered according to ASCO Guidelines. Abemaciclib must be held for at least 48 hours after the last dose of blood cell growth factors is administered and until toxicity resolves to at least Grade 2. When abemaciclib is resumed, the dose must be reduced by 1 dose level unless already performed for incidence of toxicity that led to the use of growth factor.

7.4.5 General Guidance for Interstitial lung disease (ILD)/Pneumonitis events

Interstitial lung disease (ILD) / pneumonitis has been identified as an adverse drug reaction for abemaciclib. Adverse events reported included events such as interstitial lung disease, pneumonitis, obliterative bronchiolitis, organizing pneumonia, pulmonary fibrosis. The majority of events were Grade 1 or Grade 2 with serious cases and fatal events reported.

Monitor for clinical symptoms or radiological changes indicative of ILD/pneumonitis and please ask patients to report any new or worsening pulmonary symptoms. Symptoms may include hypoxia, cough, dyspnea, or interstitial infiltrates on radiologic exams.; these symptoms should be investigated and treated as per local clinical practice and/or guidelines (including corticosteroids as appropriate). Infectious, neoplastic, and other causes for such symptoms should be excluded by means of appropriate investigations. Investigations may include imaging such as high resolution computer tomography (HRCT), bronchoalveolar lavage (BAL), and biopsy as clinically indicated (see also Table 7: refer to dose adjustment table for interstitial lung disease/pneumonitis).

Dose Modification and Management — Interstitial Lung Disease/Pneumonitis

| ose mounication and managem | ent interstitut Eung Disease/I neumonitis |
|--------------------------------------------------------------------------------------------------------------------------------------|--------------------------------------------------------------------------------------|
| CTCAE Grade | Abemaciclib Dose Modifications |
| Grade 1 or 2 | No dose modification is required. |
| Persistent or recurrent Grade 2 toxicity that does not resolve with maximal supportive measures within 7 days to baseline or Grade 1 | Hold dose until toxicity resolves to baseline or Grade 1. Resume at next lower dose. |
| Grade 3 or 4 | Discontinue abemaciclib. |

Dose Modification and Management — Nonhematologic Toxicities Excluding Diarrhea, ALT Increased, and ILD/Pneumonitis

| CTCAE Grade | Abemaciclib Dose Modifications |
|---------------------------------------------------------------------------------------------------------------------------------------------------|---------------------------------------------------------------------------------------|
| Grade 1 or 2 | No dose modification is required. |
| Persistent or recurrent Grade 2 toxicity that does not resolve with maximal supportive measures within 7 days to baseline or Grade 1 Grade 3 or 4 | Hold dose until toxicity resolves to baseline or Grade 1. Resume at next lower dose. |

